5.4.6 Additional instructions, requirements and exceptions for FLT IND
Please refer to FLT Adverse Event Reporting Guidance Document in Appendix II.

Additional Instructions

For instructions on how to specifically report events that result in persistent or significant disability/incapacity, congenital anomaly, or birth defect events via CTEP-AERS, please contact the CIP Help Desk at [contact] or [contact]. This will need to be discussed on a case-by-case basis.

FLT specific expedited reporting requirements:

Pregnancies: Pregnancies and suspected pregnancies (including a positive or inconclusive pregnancy test, regardless of age or disease state) occurring while the subject is on FLT, or within 28 days of the subject's last dose of FLT, are considered immediately reportable events. The pregnancy, suspected pregnancy, or positive/ inconclusive pregnancy test must be reported via CTEP-AERS within 24 hours of the Investigator's knowledge.

FLT specific expedited reporting exceptions:

For this protocol, the adverse events listed below (Section 5.5) do not require expedited reporting via CTEP-AERS:

- If an AE meets the reporting requirements of the protocol, and it is listed on the SPEER, it should ONLY be reported via CTEP-AERS if the grade being reported exceeds the grade listed in the parentheses next to the event.

5.4.7 Other recipients of adverse event reports and supplemental data
DCTD/NCI will notify ECOG-ACRIN/pharmaceutical collaborator(s) of all AEs reported to the FDA. Any additional written AE information requested by ECOG-ACRIN MUST be submitted to BOTH the NCI and ECOG-ACRIN.
Adverse events determined to be reportable via CTEP-AERS must also be reported by the institution, according to the local policy and procedures, to the Institutional Review Board responsible for oversight of the patient.

5.5 Comprehensive Adverse Events and Potential Risks for 3'-deoxy-3'-[F-18]fluorothymidine (FLT) (NSC 743144)

The Comprehensive Adverse Event and Potential Risks list (CAEPR) provides a single list of reported and/or potential adverse events (AE) associated with an agent using a uniform presentation of events by body system. In addition to the comprehensive list, a subset, the Agent Specific Adverse Event List (ASAEL), appears in a separate column and is identified with **bold** and *italicized* text. This subset of AEs (ASAEL) contains events that are considered 'expected' for expedited reporting purposes only. Refer to the 'CTEP, NCI Guidelines: Adverse Event Reporting Requirements' for further clarification. The CAEPR does not provide frequency data; refer to the Investigator's Brochure for this information. Below is the CAEPR for 3'-deoxy-3'-[F-18]fluorothymidine.

Version 1.0, July 1, 2010¹

Category (Body System)	Adverse Events ² with Possible Relationship to 3'-deoxy-3'-[F- 18]fluorothymidine (CTCAE v4.0 Term)	EXPECTED AEs FOR CTEP-AERS REPORTING Agent Specific Adverse Event List (ASAEL)
	No AEs reported in human studies ^{2,3} .	

¹This table will be updated as the toxicity profile of the agent is revised. Updates will be distributed to all Principal Investigators at the time of revision. The current version can be obtained by contacting [contact]. Your name, the name of the investigator, the protocol, and the agent should be included in the e-mail.

²No adverse events have been attributed to Positron-Emission Tomography (PET) imaging/diagnostic administration of [3'-deoxy-3'-[F-18]fluorothymidine at the levels described in the Investigators Brochure. Therefore, no adverse events are expected as a result of the intravenous (IV) administration of 3'-deoxy-3'-[F-18]fluorothymidine for typical PET imaging applications.

³As with many intravenously administered agents, 3'-deoxy-3'-[F-18]fluorothymidine could cause an allergic reaction that could potentially pose a threat to life (anaphylaxis). This has not been observed in limited human exposure to date. Reasonable precautions should be taken, consistent with normal radiologic and clinical facility practice. The patient should be monitored until the PET procedure is completed, and trained personnel and emergency equipment should be available per facility standards.

For purposes of informed consent regarding reasonably foreseeable risks to subjects in trials utilizing 3'-deoxy-3'-[F-18]fluorothymidine, the following potential adverse events are considered extremely rare:

[figure not shown]
- Injection-related risks that may include infection, or accidental extravasation of the dose that may lead to discomfort, localized pain, or infection.
- Risks related to allergic reaction/anaphylaxis that may be life threatening.

NOTE: As with all PET imaging agents, 3'-deoxy-3'-[F-18]fluorothymidine is a radiopharmaceutical that decays with positron emission. As such, it poses an intrinsic radiation exposure risk. However, when administered in accordance with the Investigator's Brochure as a PET imaging agent, this risk is felt to be extremely small. The organ and total body doses associated with FLT PET imaging are comparable to or lower than those associated with other widely used clinical nuclear medicine procedures.

NOTE: 3'-deoxy-3'-[F-18]fluorothymidine in combination with other agents could cause an exacerbation of any adverse event currently known to be caused by the other agent, or the combination may result in events never previously associated with either agent.

Rev. 7/17

5.6 Adverse Event Reporting Decision Tree

5.7 Duration of Follow-up

Participants will stay on the trial for at least 1 year (1 year beyond the end of the study accrual period) until they complete all trial procedures, specifically the remission bone marrow biopsy (Day 28-35 biopsy), and follow-up collection of relapse free survival and overall survival.

6. Measurement of Effect ACUTE MYELOGENOUS LEUKEMIA (AML) RESPONSE CRITERIA

6.1 Complete Remission (CR)

Requires that all of the following be present for at least 4 weeks.

- Peripheral Blood Counts
 - Neutrophil count $\geq 1.0 \times 10^9 /L$.
 - Platelet count $\geq 100 \times 10^9 /L$.
 - Reduced hemoglobin concentration or hematocrit has no bearing on remission status.
- Leukemic blasts must not be present in the peripheral blood.
- Bone Marrow Aspirate and Biopsy
 - Cellularity of bone marrow biopsy must be $> 20\%$ with maturation of all cell lines.
 - $\leq 5\%$ blasts
 - Auer rods must not be detectable.
- Extramedullary leukemia, such as CNS or soft tissue involvement, must not be present.

6.2 Partial Remission (PR)

- Requires that all of the criteria for complete remission be satisfied except that the bone marrow may contain $> 5\%$ blasts but $< 25\%$ blasts.
- If all other criteria for CR are met, then a value of $\leq 5\%$ blasts with Auer rods or abnormal morphology is considered a partial remission.

6.3 Relapse

Relapse following complete remission is defined as:

- Peripheral Blood Counts
 - Reappearance of blasts in the blood.
- Bone Marrow Aspirate and Biopsy
 - Presence of $> 5\%$ blasts, not attributable to another cause (e.g., bone marrow regeneration).
 - If there are no circulating blasts and the bone marrow contains 5% to 20% blasts, then a repeat bone marrow performed ≥ 1 week later documenting more than 5% blasts is necessary to meet the criteria for relapse.

Rev. 10/16 7. Study Parameters

7.1 Study Parameters

7.1.1 **Visit 1: Screening Visit**

- A screening assessment will occur to determine eligibility for the study.
- Patients will undergo pre-treatment bone marrow biopsy if one has not already been performed

NOTE: Pre-treatment bone marrow aspirates are required to be submitted to the ECOG-ACRIN LTRL, see Sections [7.2](#) and [11](#) for additional information. If biopsy has already been performed, peripheral blood must be submitted instead at preregistration or after registration.

- A signed consent form will be obtained prior to study trial procedures. Medical history, demographics, height, weight, and physical exam will be obtained. *If patient data are available from clinical records in the appropriate time window, they need not be repeated for the pre-study evaluation.*

Rev. 7/17

7.1.2 **Visit 1A: OPTIONAL FLT PET Imaging Study (FLT-base)**

NOTE: Per Eligibility Criteria, any pre-menopausal women or women of childbearing potential MUST not be pregnant as general practice and per institution's standard of care prior to performing any scans.

- Screening labs will be obtained within the one-week period prior to administration of FLT. Total bilirubin and creatinine should be collected per institutional standard of care. *If patient data are available from clinical records in the appropriate time window, they need not be repeated for the pre-study evaluation.*
- The optional baseline FLT PET (FLT-base) scan will take place within 1 week prior to chemotherapy.
- Specific image acquisition and reconstruction protocols will be provided in a Site Imaging Manual to participating institutions.
- An adverse event evaluation will be performed at 24 hours. Sites will be required to submit the 'PET Adverse Event Assessment' after the 24 hour monitoring period, even if there are no adverse events to report.

Rev. Add3

7.1.3 **Visit 2: MANDATORY FLT PET Imaging Study (FLT-post induction)**

NOTE: Per Eligibility Criteria, any pre-menopausal women or women of childbearing potential MUST not be pregnant as general practice and per institution's standard of care prior to performing any scans.

- Screening labs will be obtained within the one-week period prior to administration of FLT. Total bilirubin and creatinine should be

Rev. Add3

collected per institutional standard of care. *If patient data are available from clinical records in the appropriate time window, they need not be repeated for the pre-study evaluation.*

- The post treatment FLT PET (FLT-post induction) scan will take place after completion of the induction therapy and within 3 days before or after nadir bone marrow (approximately Days 10-17 after the initiation of the first cycle of the chemotherapy and prior to re-induction if required).
- An adverse event evaluation will be performed at 24 hours (+/- 4 hours). Sites will be required to submit the 'PET Adverse Event Assessment' after the 24 hour monitoring period, even if there are no adverse events to report.

Rev. Add3

7.1.4

Visit 3: Nadir Bone Marrow at Day 10 to 17

Following completion of induction chemotherapy, the subject will undergo standard of care nadir bone marrow evaluation (Day 14 bone marrow biopsy) 7-10 days after the completion of induction chemotherapy. Local pathology report data will be collected from this time point as part of follow up for the EAI141 study.

7.1.5

Visit 4: Remission Bone Marrow at Day 28 to 35

Participants will undergo remission bone marrow biopsy at Day 28 to 35 after initial induction chemotherapy, if reinduction chemotherapy is not administered; at Day 28 to 35 after reinduction chemotherapy if reinduction chemotherapy was administered; local pathology report data will be collected from this time point as part of follow up for the EAI141 study.

NOTE: Remission specimens are REQUIRED to be submitted to ECOG-ACRIN LTRL, see sections [7.2](#) and [11](#) for additional information.

7.1.6

Sharing of Results

The final results of the study will be shared with the participating centers at the completion of the study. With agreement between the patient and the treating physician, and at the discretion of the participating center, the treating physician may share the experimental results of the FLT PET/CT imaging scans with the participant. The sharing of the informal results should be done with caution, as the FLT PET/CT is still experimental and the significance of these results is unknown. **The results from the FLT PET/CT scans should not be part of the patient's medical record and should not be used to direct or change therapy.** We emphasize that sharing of imaging results with patients remains optional and at the discretion of the participating center, the patient and the treating physician.

Study Procedures Table

Study Procedures	VISIT 1: SCREENING	VISIT 1A: OPTIONAL Baseline FLT PET/CT (FLT-base) ²	VISIT 2: Post-Treatment FLT PET/CT (FLT-post) ³	VISIT 3: Nadir Bone Marrow (Day 10 to 17) ⁴	VISIT 4: Remission Bone Marrow (Day 28 to 35) ⁵
Informed Consent	X				
Demographics ¹	X				
Medical History ¹	X				
Height ¹	X				
Weight ¹	X	X	X	X	
Physical Exam ¹	X				
Pre-Scan Pregnancy and Serum Creatinine Evaluations ¹		X		X	
[F-18]FLT PET/CT ⁶		X	X		
Bone Marrow Biopsy	X			X	X
Other Clinical Evaluations ⁷	X			X	X
Adverse Event Evaluation		X		X	
Biological Sample Submissions					See Sections 7.2 and 11
Follow-Up Data Collection					Standard Practice Clinical Data Will Be Collected for 1 Year from Enrollment of the Last Participated Accrued to the Study

Rev. 10/16

Rev. Add3

- If patient data are available from clinical records in the appropriate time window, they will not be repeated for the pre-study evaluation. Total bilirubin and creatinine should be collected per institutional standard of care before FLT PET/CT.
- Baseline FLT PET/CT imaging (FLT-base) is **optional**, and must be done within 1 week prior to initiation of therapy protocol.
- Post-treatment FLT PET/CT imaging (FLT-post) must be done after the completion of the induction chemotherapy and within 3 days before or after nadir bone marrow and prior to reinduction if required (Days 10-17 after the initiation of the first cycle of the chemotherapy and prior to reinduction if required)
- Nadir bone marrow will be performed per standard clinical practice, typically within 7-10 days after the completion of induction therapy.
- Remission bone marrow will be performed per standard clinical practice, typically at Day 28-35 after treatment began and upon count recovery.
- NOTE:** Per Eligibility Criteria, any pre-menopausal women or women of childbearing potential MUST not be pregnant as general practice and per institution's standard of care prior to performing any scans.
- Other clinical evaluations include: Cytogenetics and molecular studies as mandated by the treatment study in which the patient is enrolled. If the patient is not enrolled in another study, the cytogenetic and molecular studies should be done according to the treating institution's standard of care.

Rev. 10/16

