		
PI Response: The study team is no longer moving forward with the new exploratory objectives involving FLT PET after reinduction. Based on the statistics of the patients accrued so far, we would expect less than 10 patients that would receive re-induction and were candidates for a potential post re-induction scan.
 
3. What are the biologic and clinical differences between those patients who do and do not receive reinduction?
 
PI Response: Patients with resistant disease that requires re-induction chemotherapy often have high risk features such as poor risk cytogenetics, poor risk molecular findings (i.e. FLT3), or age > 60 years.
 
4. What is the anticipated accrual into each of the 2 optional FLT arms and will either reach any statistical significance?
 
PI Response: The study team is no longer moving forward with the new exploratory objectives involving FLT PET after reinduction.
 
For the requested statistics, please reference the supplemental data provided separate from this resubmission. With regard to the optional baseline FLT scan: we initially projected that half of the cohort would be scanned at T=0 (or baseline) and powered up the study for the corresponding aim. However, the monitoring of our data showed that the actual rate was lower than expected, thus, this won't reach statistical significance (the power calculation was mainly aimed to provide statistical significance for the primary endpoint). However, we anticipate that there will be a sufficient number of patients for providing a strong rationale for future follow-up studies specifically focusing on these exploratory imaging endpoints.
 
5. Will the Bone Marrow Biopsy at Day 28-35 always be post reinduction FLT (for those patients in which this late FLT scan is performed)? Section 4.8 (and in Section 5; multiple places) suggests that this is not necessarily the case. Is it not possible that FLT scan could be positive simply due to effects of recent bone marrow biopsy?
 
PI Response: The study team is no longer moving forward with the new exploratory objectives involving FLT PET after reinduction.
 
6. What is the expected time period from induction to reinduction?
 
PI Response: Reinduction chemotherapy is started soon after the day 14 marrow if there is persistent disease. The day 14 (nadir) marrow is performed 14 days after the initial chemotherapy is started.

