3. Post-Treatment Imaging is mandatory and must be completed 10-17 days after initiation of first induction cycle and prior to reinduction.
4. Nadir Bone Marrow should be completed 7-10 days after completion of induction therapy. Remission Bone Marrow should be completed 28-35 days after initiation of first induction therapy
5. Remission bone marrow aspirate should be sent for central analysis.
6. Participants will be followed for up to 1 year beyond the end of the accrual period.

Rev. 10/16

STUDY OBJECTIVES

Primary Objective

To evaluate the negative predictive value (NPV) of post-treatment FLT PET/CT imaging for complete remission (CR) in patients receiving induction chemotherapy for acute myeloid leukemia (AML).

Secondary Objectives

- To evaluate the positive predictive value (PPV) of post-treatment FLT PET/CT imaging for complete remission;
- To estimate the sensitivity and specificity of post-treatment FLT PET/CT imaging for detecting complete remission;
- To correlate FLT PET/CT imaging with biologic correlates (MRD Assessment)
- To correlate FLT PET/CT imaging with relapse-free survival and overall survival.

Rev. Add3

Exploratory Objectives

- To evaluate pre-treatment FLT PET/CT imaging as a predictor of complete remission;
- To evaluate the change between pre-treatment and post-treatment FLT PET/CT imaging as a predictor of complete remission;

ELIGIBILITY (see Section 3 for details)

Patients must be 18 years old and have previously untreated AML and be candidates for intensive induction chemotherapy. Patients are allowed to have had prior hydroxyurea. Patients must not have acute promyelocytic leukemia (APL) and must not have evidence of t(15;17)(q22;q21). Patients must have an ECOG performance status of 0-3 (restricted to ECOG PS 0-2 if age > 70 years).

SAMPLE SIZE

Rev. Add3

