1.2 FLT PET/CT in AML: A Potential Early Predictor of Response

Acute myeloid leukemia (AML) is a devastating, clinically heterogeneous disease for which improved treatment strategies are needed. Long-term cure depends upon the ability to induce a complete remission, followed by consolidation treatment with either chemotherapy or stem cell transplantation. Standard induction chemotherapy is administered over 7 days, after which treatment response is usually assessed at two time points after initiation of chemotherapy: the nadir bone marrow at approximately Day 14, and at the time of peripheral blood count recovery, which is at approximately Day 28.

If the Day 14 marrow has a significant number of residual leukemia blasts, a second induction therapy course can be administered. If the Day 14 marrow is hypoplastic, the patient will receive no further treatment at that time and the counts will be allowed to recover. However, the Day 14 marrow has limitations as a marker of the success of induction therapy. A substantial number of patients with no blasts in the nadir marrow will not achieve remission (a false negative result). On the other hand, some patients who have residual disease in the marrow at Day 14 will eventually achieve a complete remission (CR) even without another induction chemotherapy course (a false positive result). A review of the literature showed the nadir marrow as a test has a false negative rate ranging from 21% to 33% and a false positive rate of 19% to 36%. Possible explanations for these error rates include a fairly limited sample of an extensive marrow space, heterogeneity of AML involvement in the bone marrow, and lack of clarity about whether residual blasts are in the process of dying at the time of assessment or whether they are blasts resistant to chemotherapy.

A better early predictor of residual disease that assesses chemotherapy effectiveness would give clinicians and patients an opportunity to modify therapeutic strategies. Preliminary, single-center data support proliferation imaging using an investigational agent known as 3'-deoxy-3'-¹⁸F-fluorothymidine (FLT) in positron emission tomography/computed tomography (PET/CT) as a method of assessing the entire burden of disease and avoid the confounding

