9.11 Image Analysis

A central review and analysis of all FLT PET/CT imaging will be performed at the ACR Imaging Core Laboratory in coordination with the University of Wisconsin Image Analysis Core (IMAC). The centralized imaging analysis will be used for endpoint calculations. Radiologists will perform local reads of the images to help guide central review. Central review will subsequently be completed; data will be shared at the culmination of the study.

10. Statistical Considerations

The overall objective of this trial is to evaluate the negative predictive value of post-treatment FLT PET/CT imaging for complete remission (CR) in comparison with blast counts from bone marrow biopsy (BMBX) at Day 14.

Definition of complete remission (CR): The CR designation requires that the patient achieve the morphologic leukemia-free state and have an absolute neutrophil count of more than 1,000/uL and platelets of greater than 100,000/uL. Hemoglobin concentration or hematocrit has no bearing on remission status, although the patient must be independent of transfusions. Occasionally, a rare peripheral blood blast may be identified during regeneration; however, if the patient is in CR, the bone marrow would have less than 5% blasts and no Auer rods [4].

Definitions of FLT Positivity and Negativity for CR:

- FLT PET “positive” $\rightarrow \text{SUV}_{\max} \leq 7$
- FLT PET “negative” $\rightarrow \text{SUV}_{\max} > 7$

The post-treatment FLT PET/CT needs to be conducted **within three days** before or after the nadir bone marrow biopsy (between Days 10-17 after initiation of first induction cycle and prior to reinduction). After the imaging analysis to collect SUV_{\max} , we define a positive testing result as a low uptake value, which corresponds to the lower blast count in the BMBX.

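### Schema note 4 times the remission marrow from first induction for every patient, 7.1.5 times it from reinduction when that is given; the two windows cannot overlap, and 10.1.1 does not name the marrow that decides CR

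*Combined protocol and SAP*

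**What the plan says.** The Schema and the visit description give different clocks for the same procedure.

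- Schema note 4: "Remission Bone Marrow should be completed 28-35 days after initiation of first induction therapy". It makes no exception for reinduced patients.
- Section 7.1.5 counts from initial induction if there is no reinduction, and otherwise "at Day 28 to 35 after reinduction chemotherapy if reinduction chemotherapy was administered". The list of changes shows that Addendum 3 revised this paragraph to clarify the reinduction case. The same addendum edited Schema note 3; note 4 still counts from first induction.
- Schema note 3: the post-treatment scan "must be completed 10-17 days after initiation of first induction cycle and prior to reinduction".
- Study Procedures Table, footnote 5: the remission marrow is done "typically at Day 28-35 after treatment began and upon count recovery". Section 9.9.2 words it the same way. Neither mentions reinduction.
- Sections 5 and 5.3 allow one or two induction cycles, so reinduction is within the plan.
- Section 10 defines CR by marrow findings and by an "absolute neutrophil count of more than 1,000/uL and platelets of greater than 100,000/uL". Neither that definition nor 10.1.1 names a time point or a course.

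**The concern.** The remission marrow decides CR, and CR decides the primary endpoint. A reinduced patient cannot have one marrow that meets both Schema note 4 and 7.1.5. Section 1.2 puts the nadir at about Day 14 of a course and the response marrow "at the time of peripheral blood count recovery, which is at approximately Day 28". A marrow taken on the Schema clock would fall near the nadir of the second course, when the neutrophil and platelet thresholds for CR are unlikely to be met. A patient who goes on to CR could be entered as non-CR.

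The direction is known. FLT-negative means SUVmax above 7, and the NPV is the proportion of FLT-negative patients without CR. Turning a CR into a non-CR in that group can only increase the NPV, which favours FLT in a one-sided test against 0.64.

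**Working it through.** **Calendar.** Let reinduction start on Day s, counted from the start of first induction.

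- Schema window on the first-induction clock: Day 28 to 35.
- 7.1.5 window on the first-induction clock: Day s+28 to s+35.
- Schema window on the second-course clock: Day 28-s to 35-s.

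The windows meet only if s + 28 ≤ 35, that is s ≤ 7. The scan is on Day 10 or later and comes before reinduction, so s ≥ 10 for any patient scanned to protocol. The usual start is not given as a day. The sponsor's reply to the review comments says only: "Reinduction chemotherapy is started soon after the day 14 marrow if there is persistent disease". I take Day 14-17 as the assumption.

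| Reinduction start (s) | 7.1.5 window, first-induction clock | Days from Schema close (Day 35) to 7.1.5 opening | Schema window, second-course clock |
|---|---|---|---|
| Day 10 (earliest possible) | Day 38-45 | 3 | Day 18-25 |
| Day 14 | Day 42-49 | 7 | Day 14-21 |
| Day 17 | Day 45-52 | 10 | Day 11-18 |

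For s from 14 to 17 the Schema window covers Day 11-21 of the second course. If 'after reinduction' means after its completion, the gap widens.

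**The plan's own test, reproduced.** Inputs from Section 10: n = 21 FLT-negative patients, null NPV 0.64, alternative 0.85, one-sided 0.10, exact binomial. Let X be the number of non-CR among the 21.

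- P(X ≥ 17 | 0.64) = 0.0779, which is at most 0.10.
- P(X ≥ 16 | 0.64) = 0.1753, which is above 0.10. The critical value is therefore 17.
- P(X ≥ 17 | 0.85) = 0.8025, which matches the stated 80% power.

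The sample size is not in question.

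**What a miscoding does.** If k of the patients counted as non-CR are really CR, the count falls by k.

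| Coded non-CR count | p as coded | Effect of correction |
|---|---|---|
| 17 | 0.078 | one correction gives 16, p = 0.175; significance lost |
| 18 | 0.027 | one correction gives 17, p = 0.078, still significant; two give 16, p = 0.175 |
| 19 or more | below 0.027 | two corrections leave at least 17; still significant |

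**How many patients.** The documents give no count of reinduced, FLT-negative patients who reach CR. The nearest figure is the sponsor's reply: "we would expect less than 10 patients that would receive re-induction", restricted there to candidates for a post-reinduction scan. It is not split by FLT result or by outcome.

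**The case against.** The case against giving this weight is good in several respects. Section 7.1.5 is the operative visit instruction and was revised to cover this case, so the sponsor's intention is clear. Schema note 4 is a summary note worded as a recommendation, whereas note 3 is worded as a requirement. Footnote 5 and 9.9.2 tie the marrow to standard practice and count recovery, which works against sampling at a second nadir. Under 7.1.5 each patient has one remission marrow, so Section 10 has only one CR status to use. The changes in p-value would follow from any coding error in an exact test of 21 patients.

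All of that stands, and it limits the size of the point. It does not remove it. Note 4 is current text, it gives a wrong instruction for reinduced patients, and Section 10 contains nothing that would override it.

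A reader might infer that footnote 5 and 9.9.2 also contradict 7.1.5. They do not: both say what is typical and refer to count recovery, and lack only the exception. A reader might also infer that the primary NPV is inflated. The documents do not support that, because no affected patient is shown and no number can be derived. Nor does the conflict call for NPV and PPV split by reinduction status, or for a sensitivity analysis counting reinduced patients as non-CR. Neither follows from a timing conflict, and the second can only raise the NPV or leave it unchanged, so it could not reveal a bias in favour of FLT.

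**Conclusion.** The conflict is real and is present in the current text. For every reinduction date compatible with the mandatory scan, the two windows are disjoint: Day 28-35 against Day 38 or later. That part needs no assumption beyond the scan coming before reinduction on Day 10 or later. The statement that the Schema marrow falls on about Day 11-21 of the second course assumes reinduction on Day 14-17.

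The effect on the primary result is possible but unquantified. It requires a site to follow the Schema rather than 7.1.5, an FLT-negative patient who later reaches CR, and no later marrow used in its place. If it happens, the error favours FLT. One miscoding changes the conclusion only at a coded count of exactly 17 of 21; two do so at 17 or 18. This should be corrected because the instruction is wrong and the correction is short, not because bias has been shown.

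**What to change.** 1. Change Schema note 4 to: '28-35 days after initiation of first induction, or 28-35 days after reinduction if reinduction is given.'
2. Add the same exception to Study Procedures Table footnote 5 and to 9.9.2, for consistency.
3. Add to 10.1.1: 'CR for the primary NPV is CR status at the Visit 4 marrow after the last induction course given (7.1.5).'
4. Report how many reinduced patients had only a marrow on the first-induction clock, with their FLT result. This shows whether the problem occurred and in which group.

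The cost is wording in four places and one count from treatment and pathology data already collected. The sample size and the test do not change. The small downside is that a later marrow may be missed somewhat more often. Section 10 attributes about half of the roughly 38% attrition to failed remission marrows, so this should be watched. Section 7.1.5 already requires the later marrow, so the extra burden falls only where sites have been following the Schema.
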